## 5. STUDY DESIGN AND METHODS OF DATA COLLECTION AND DATA ANALYSIS

### Part A: Clinical Evaluation

[figure not shown]
This is a prospective, multi-centre healthcare service delivery study with the primary objective of assessing the effectiveness of AI immediate read and worklist prioritisation for immediate review on the time to diagnosis of lung cancer and the time to CT chest following abnormal CXR. The study will be conducted over a 12-month period at eight NHS Trusts in England. qXR, a class IIa CE certified deep learning algorithm already in routine clinical use in some NHS Trusts, will be used in this study. All patients in the study will have their CXRs read by qXR. The only difference is the timing of the information from the AI. The process adopted in radiology departments is that the patient attends for a CXR and it is performed by a radiographer. The radiographer may, at their discretion flag abnormalities that may require further action and this may result in a CT scan being done, sometimes on the same day as is a preferred option in the NOLCP. The radiographer flag can also happen for any other (non-cancer) findings where they consider that action is potentially needed. The usual clinical pathway will be followed where action is confirmed to be necessary or optimal. Where there is no flag, the CXR is later reported by a radiologist or reporting radiographer. This study is testing whether having an AI immediate tag influences that process and shortens time to diagnosis. The pathway is shown on the study flowchart (page 10).

AI clinical decision support will be available to the reporting practitioner (consultant radiologist, specialist registrar or reporting radiographer) for all CXRs. The intervention is the timing of the CXR alert from the AI, on intervention (worklist prioritisation for immediate report) and non-intervention (routine reporting time) days. On intervention days, an active notification will be sent to the worklist for any 'qXR-suspected-abnormal cases, so these can be prioritised for immediate reporting. Pre-allocation to intervention (qXR AI support at the time of CXR acquisition and worklist prioritisation for immediate CXR review) and routine care (normal reporting with

SHORT TITLE/ACRONYM: LungIMPACT  
IRAS: 317009

qXR read available) will occur using random sampling (Monday – Friday when routine imaging is performed). All patients over 18 years will have qXR decision support available. Patients will receive routine care, no additional diagnostic tests will be performed. Data will be collected from existing routine clinical data sources. All imaging (CXR or CT) will be performed as part of routine care, and no additional radiation exposure will be required. The reporting practitioner will have the AI decision support information for all cases and all days, the intervention is only the timing of the AI information (immediate reporting or with usual reporting). The reporting practitioner can choose to accept the alert and refer the patient for CT chest and/or referral onto the lung cancer pathway where appropriate. Patients who are referred for CT will follow the current CT and post-CT pathways of the participating clinical sites, which may include placing them on a cancer pathway. On non-notification days, the AI tool information will be available at the time the CXRs are reporting by the reporting practitioner (Figure 1). The PACS will have both the original image and qXR secondary capture showing the AI attention point.

**Figure 1: Intervention and non-intervention days in RIS**

Where AI flagging of abnormalities are rejected by the reporting practitioner they will be reviewed by an expert panel of thoracic radiologists at a weekly interval at each study site according to pre-defined thresholds depending on patient risk/safety (Table 5).

Radiographers will follow their normal duty of care on both notification and non-notification days. Although it is unlikely, undue reliance on AI on notification days and extra vigilance on non-notification days will be measured through numbers actioned by radiographers and the discrepancy check.

**Table 5. Proportion of discordant cases to undergo thoracic radiologist review**

Abnormality	Proportion
Blunted CP	1,000 CXRs
Cardiomegaly	1,000 CXRs
Cavity	All
Consolidation	All
Fibrosis	20%
Hilar enlargement	All
Nodule	All
Opacity	All
Pleural effusion	20%
Pneumothorax	All

Cases that are flagged (in either arm) as positive but not taken up for further testing will be reviewed and patients with CXRs suspicious for cancer will be called back for further testing. This is done in both arms of the study and is an additional safety check; this is routine clinical practice. The proposed review/recall methodology is a form of radiology peer review, advocated as an effective method of quality assurance. Double reading and recall where appropriate is not novel, for example it is used as standard as part of the breast cancer screening programme.

Variables collected:

Only data collected for routine care will be used and no additional data will be collected. No patient identifiable data will be available outside of the clinical care team; all data will be pseudonymised prior to analysis by the independent statistician. qTrack will be used as the trial management database; it cannot be accessed by the Qure Team. Variables are presented in Table 6.

**Table 6. Routine data used for analysis**

Variables	Source
AI support at the time of CXR acquisition and prioritisation for review	Auto-filled from the sequence generated
Age	DICOM metadata
Sex	DICOM metadata
AI CXR finding	Qure backend - qTrack
CXR report finding/diagnosis	Automated NLP feeding into qTrack
Time of CXR referral	DICOM metadata
CXR taken time	DICOM metadata
CXR report generation time	QTrack
Referral to CT- Yes/No	Cancer nurse/imaging staff from PACS/RIS
Date of CT report	Cancer nurse/imaging staff from PACS/RIS
Diagnosis	Cancer nurse/imaging staff from PACS/RIS
Date of diagnosis of lung cancer	Cancer Waiting Time database
Stage of lung cancer	Cancer Waiting Time database
Date of 2WW referral	Cancer Waiting Time database, automated (.csv if possible)
date of decision to treat	Cancer Waiting Time database
Treatment start date	Cancer Waiting Time database
discharge date	Cancer Waiting Time database
qXR-CXR report agreement	qCheck
Outcome of discordant expert review	Template circulated with outcomes based on CT template
Reporting Practitioner Study ID	DICOM metadata
Reporting practitioner profession	Radiology department staff record

*Health Economic Analysis*

An economic evaluation will be conducted to estimate the cost-effectiveness of artificial intelligence (AI)-based triaging of CXRs for lung cancer diagnosis from the NHS perspective. We shall analyse the cost-effectiveness of AI-based triaging compared to routine reporting. We shall develop a decision-analytic model using available evidence on lung cancer diagnosis and healthcare professionals' expert opinion. The probabilities used in the model will be identified from the clinical study and the literature (e.g., meta-analyses), and national datasets.

Health outcomes for the economic assessment shall be measured in terms of difference in days to diagnosis (time to full work up and decision to refer for treatment / best supportive care at the multidisciplinary meeting) and the stage of diagnosis. Additionally, the impact of early-stage diagnosis on quality of life shall also be incorporated if relevant data to the UK setting will become available from the narrative literature review. The cost parameters required to populate the model will be identified from national datasets, such as the NHS reference costs. Healthcare resource use will be identified as part of staff experience interviews and based on the discussion with the clinical experts in the research team.

We shall assess costs primarily from the perspective of the NHS and personal social services. Thus, we shall estimate the cost to implement the AI support at the time of CXR acquisition and prioritisation for immediate review of CXRs, the training costs, and the maintenance costs, as well as the cost of the usual practice. We shall derive unit costs from standard sources. The time horizon of the main analysis will be 60 days since the clinical study will measure the short-term impacts of the intervention. An additional analysis adopting a lifetime horizon could be potentially conducted if there is sufficient evidence and data (e.g. QALYs). If a lifetime horizon will be adopted costs and outcomes after the first year shall be discounted at a 3.5% discount rate as recommended by NICE. All costs will be reported in 2022 GBP.

Cost-effectiveness of AI support at the time of CXR acquisition and prioritisation for immediate review of CXRs shall be assessed comparing the costs and outcomes of the new intervention and the usual practice. We shall estimate the difference in costs per patient screened, cost per patient diagnosed, and costs per percentage increase in early diagnosis. This will be compared with the difference in effectiveness (e.g. less time to decisions, increase in early-stage diagnosis). Contingent on appropriate data availability in the literature on the impact of early diagnosis on quality of life, we might be able to estimate the difference in costs per additional QALY gained.

SHORT TITLE/ACRONYM: LungIMPACT  
IRAS: 317009

If the intervention arm is more effective (less time to decisions, increase in early-stage diagnosis) and less costly, then the intervention would be considered dominant over the comparator. If the intervention provides the same level of effectiveness at a lower cost, it would be considered cost-effective compared to the comparator. If the intervention is more costly and more effective, then the decision-makers need to consider some other factors, such as the availability of radiologists.

A Return-on-investment (ROI) analysis, shall be undertaken, identifying net benefits relative to net costs. We shall estimate payback in different time periods (e. g. one year, five years). ROI demonstrates whether a new technology or service offers value for money, and it is used by local decision-makers. The ROI analysis would help NHS to identify net benefits relative to costs demonstrating value for use by decision-makers.

Deterministic and probabilistic sensitivity analyses will be conducted to explore parameter uncertainty and the uncertainties caused by methodological assumptions. Deterministic sensitivity analysis will identify the key parameters that have a significant impact on the findings, varying one parameter at a time. The probabilistic sensitivity analysis will estimate the confidence intervals for the cost-saving and return on investment estimates, using Monte Carlo simulation.

SHORT TITLE/ACRONYM: LungIMPACT  
IRAS: 317009

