## 2. RATIONALE

Recently published work performed by members of the study team (Woznitza *et al radioX*) found that immediate radiographer CXR reporting and triage straight to CT significantly reduced time to diagnosis of lung cancer by almost half from a median of 63 days from CXR, to 32 days, ( $p = 0.03$ ) compared to routine CXR reporting once the patient has left the department. This demonstrated that immediate CXR reporting pathway is feasible and beneficial. A trend for fewer urgent referrals being made to respiratory medicine was also found, with a higher proportion of cancer diagnoses made in those with immediate CXR reporting (18% vs 12%;  $p = 0.12$ ). What is unclear is if the findings of this single site study with a small number of lung cancers ( $n=49$ ) is replicable in other settings or scalable at a system level. Benefits of other interventions successful in single clinical sites are not always transferrable when evaluated in multi-site trials for many reasons, including implementation barriers. Since immediate reporting has resource and workforce implications, it is crucial that if immediate reporting is to be rolled out nationally, it is done so based on robust evidence.

Nearly two million CXRs referred from primary care are performed annually in England and CXR is one of the most frequently performed investigations. Not all CXRs will have findings suspicious for cancer, and this may be an incidental finding (CXR requested for a reason other than suspected cancer). One way to optimise the limited imaging workforce could be to use an artificial intelligence (AI) tool as assistance in decisions to triage CXRs referred from primary care that have findings suspicious for lung cancer. This would enable immediate flagging and reporting to be prioritised for patients most likely to benefit from a same-day CT scan. AI clinical decision support was identified as one way to reduce observer variability in CXR interpretation by NICE as well as supporting current NICE care pathways for suspected cancer, chronic obstructive pulmonary disease, cystic fibrosis, idiopathic pulmonary fibrosis and tuberculosis.

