### 7.3.1 Size of sample

#### Part A

The primary endpoints of this study are the difference in median time between CXRs suspicious for lung cancer and CT chest and the difference in median time to lung cancer diagnosis between routine reporting with AI available and AI support at the time of CXR acquisition and prioritisation for immediate review of CXRs reporting arms. The expected prevalence of lung cancer in this cohort (primary care referrals for CXR) is 0.6%. Thus for 150,000 CXRs this will lead to the detection of about 900 cancer cases. Using data from previous work, the median time to lung cancer diagnosis was 63 days in the standard reporting group and if we use a conservative reduction of 10 days, with 95% power we would need 265 cases per group (Table 6). Most likely, the time to diagnosis is going to be greater than 10 days such that the sample size will give us plenty of power to detect a difference between the groups on time to diagnosis. Considering that 30% of lung cancer patients die within 90 days of diagnosis, a 10 or more-day difference is clinically significant (Table 7).

The co-primary endpoint of this study is time between an abnormal CXR that is suspicious for lung cancer to CT chest. Based on the NHS Diagnostic Imaging Dataset between 4,000-4,500 CT chest scans referred from primary care are expected during the study period at the clinical sites, median time for England (CT chest request to test) is 14 days, but this data is not segregated between urgent scans and those that are routine or for follow up. The mean and standard deviation of time between abnormal CXR and CT chest are not known for either the intervention (AI support at the time of CXR acquisition and prioritisation for immediate review of CXRs) or routine CXR reporting with AI available. Cohen's d (effect size) was used to estimate sample size with power 0.1, 0.3 and 0.5 are considered small, moderate and large effect size. Assuming approximately equal distribution (Nnotification:Nstandard as 0.8 to 1.2) of the number of scans taken, the estimated 4,000 CT chest scans will give adequate power to detect even the smallest effect size (Cohen's d = 0.1; Figure 2). We have defined a clinically meaningful difference in time from abnormal to CT chest as 3 days, using the maximum time recommended in the NOLCP.

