**Figure 2. Sample size calculation for time from abnormal CXR to CT chest (days)**

We would also like to have enough numbers to examine the secondary outcome if the strength of the agreement between qXR and CXR reporter in normal/abnormal classification. Based on an anticipated abnormal prevalence 40% of primary care CXRs and as measured by kappa (hypothesized as 0.82) an absolute precision of 2%, we would need 3,601 patients included. Not only is the time to diagnosis is important but also the accuracy of diagnosis. The study will also have enough number to report on agreement of individual abnormality with the above precision.

Table 7. Sample size calculation for time (in days) to diagnosis of lung cancer

	Median Days to diagnosis	Hazard	Sample Size	Total sample size	POWER
Routine	38	0.018	201	402	90
qXR immediate	28	0.025			
Routine	32	0.022	156	312	90
qXR immediate	22	0.032			
Routine	63	0.011	759	1518	90
qXR immediate	53	0.013			
Routine	63	0.011	567	1134	80
qXR immediate	53	0.013			
Routine	20	0.035	51	102	90
qXR immediate	10	0.0693			

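### The main economic analysis stops at 60 days, short of the 63-day planning median for diagnosis under routine reporting, and its comparator is not tied to the trial's control arm

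*Protocol*

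**What the plan says.** **Horizon.** Protocol section 5, Health Economic Analysis: "The time horizon of the main analysis will be 60 days since the clinical study will measure the short-term impacts of the intervention". No other reason is given, and the Protocol sets no 60-day follow-up anywhere else; the study runs for 12 months. A lifetime analysis is possible if data allow, and return on investment is to be reported over periods such as one and five years.

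**Economic outcomes.** The same subsection measures benefit as the difference in days to diagnosis and as stage. It takes diagnosis to mean that work-up is complete and the multidisciplinary meeting has decided on treatment or supportive care. The ratios are cost per patient screened, per patient diagnosed, and per percentage increase in early diagnosis.

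**Planning times.** Section 7.3.1 states that "the median time to lung cancer diagnosis was 63 days in the standard reporting group" and sizes the study "if we use a conservative reduction of 10 days". Section 2 shows the origin: an earlier single-site study with 49 lung cancers, in which time to diagnosis fell "from a median of 63 days from CXR, to 32 days". Table 7 carries the assumption ("Routine 63 0.011 759 1518 90", paired with 53 days) and also lists routine medians of 38, 32 and 20 days, each with a 10-day reduction.

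**Comparator.** The economic text says: "We shall analyse the cost-effectiveness of AI-based triaging compared to routine reporting". It lists implementation, training and maintenance costs for the AI pathway, "as well as the cost of the usual practice". Earlier in section 5 the design is described differently: "The reporting practitioner will have the AI decision support information for all cases and all days".

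**The concern.** An economic horizon should be long enough for the outcomes in the ratio to occur. Here the horizon is shorter than the time by which half the routine-arm cancers are expected to be diagnosed. Two distortions follow if the rule is applied as written.

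- A cancer found on day 55 in one arm and day 65 in the other counts as a diagnosis in the first and as none in the second. A gain in time becomes a gain in number, which is what cost per patient diagnosed divides by. The early-stage percentage is exposed in the same way.
- Work-up costs after day 60 are dropped, and they fall more heavily in the slower arm.

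The comparator raises a second, smaller matter. The trial effect is that of an immediate alert against the same AI read seen later. If usual practice were costed without AI, the incremental cost would answer a different question from the incremental effect. Cost-effectiveness is one of the Protocol's listed research questions, so both points should be settled before the analysis starts.

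**Working it through.** **1. Inputs.** Horizon 60 days (section 5). Medians 63 v 53, 38 v 28, 32 v 22 and 20 v 10 days (Table 7), and 63 v 32 days from the earlier study (section 2). About 900 cancers (section 7.3.1). Assumed: 450 per arm, the clock starting at the CXR, exponential times, and every cancer eventually diagnosed in both arms.

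**2. Reproducing Table 7.** Hazard = ln 2 / median: 0.693/63 = 0.0110 and 0.693/53 = 0.0131, as stated. Freedman's formula with the rounded hazards, two-sided 5% (assumed) and every patient an event:

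events = (1.960 + 1.282)² × [(0.013 + 0.011)/(0.013 − 0.011)]² = 10.507 × 12² = 1,513, rounded up to 1,514, or 757 per arm (stated 759).

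At 80% power the result is 565.5 per arm (stated 567). The other rows give 198.5, 153.5 and 49 (stated 201, 156 and 51). The exponential model is therefore the plan's own. The narrative's 265 per group does not match the 63 v 53 rows; that is a separate matter and is not used here.

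**3. Cutting that model at day 60.** With median m and horizon H:

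- share diagnosed = 1 − 2^(−H/m)
- mean time within the horizon = (m/ln 2) × (1 − 2^(−H/m))

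For 63 v 53 days:

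- Routine share: 1 − 2^(−60/63) = 0.483. Intervention share: 1 − 2^(−60/53) = 0.544.
- Diagnosed after day 60: 450 × (0.517 + 0.456) = about 438 of 900.
- Mean within 60 days: 90.9 × 0.483 = 43.9 and 76.5 × 0.544 = 41.6, a difference of 2.3 days.
- Untruncated mean difference: (63 − 53)/0.693 = 14.4 days. Share kept: 2.3/14.4 = 16%.

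| Medians, routine v immediate | Diagnosed by day 60 | Mean difference kept (days) | Share kept |
|---|---|---|---|
| 63 v 53 | 48% v 54% | 2.3 of 14.4 | 16% |
| 38 v 28 | 67% v 77% | 5.2 of 14.4 | 36% |
| 32 v 22 | 73% v 85% | 6.6 of 14.4 | 46% |
| 20 v 10 | 88% v 98% | 11.1 of 14.4 | 77% |
| 63 v 32 (earlier study) | 48% v 73% | 10.3 of 44.7 | 23% |

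Because all cancers are eventually diagnosed in this model, the gap in the second column is timing alone. It is 6 points at 63 v 53 days and 11 to 12 points in the other Table 7 rows.

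**4. Longer horizons, 63 v 53 days.**

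| Horizon (days) | Diagnosed | Gap (points) | Mean difference kept (days) |
|---|---|---|---|
| 60 | 48% v 54% | 6.1 | 2.3 |
| 90 | 63% v 69% | 6.3 | 4.2 |
| 120 | 73% v 79% | 5.9 | 6.1 |
| 180 | 86% v 91% | 4.3 | 9.2 |
| 365 | 98% v 99% | 1.0 | 13.4 |

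**5. Comparator, passages side by side.** Sections 4.2 and 5 define the control as routine reporting with the AI read available, timing being the only difference. Section 5 also applies the review of rejected AI findings in both arms. The Health Economic Analysis text speaks of routine reporting and usual practice without saying whether these include qXR, and itemises AI costs only for the intervention. No AI unit cost is given, so no figure for a mismatch can be worked out.

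**The case against.** **On the horizon.** The 63 days is a planning value from a small earlier study and not a result of this trial; three other Table 7 scenarios put the routine median below 60 days. This stands, and it is why a range is shown. It does not remove the problem, since every scenario loses part of the difference.

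The evaluation is also a decision-analytic model that draws on the trial, the literature and national datasets, and Table 6 puts no 60-day limit on collecting diagnosis dates or stage. A reader might infer that the analysis cannot observe its own outcome, or that stage will be missing for about half the cancers. The Protocol does not support that: it would hold only if the model inputs were themselves cut at day 60. But the text does not say that later times enter the main result either, and a stated 60-day horizon would ordinarily exclude them.

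The payback periods, the conditional lifetime analysis and the planned sensitivity analyses soften the consequence. None of them replaces the main ratio.

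**On the comparator.** A reader might infer that the control arm is costed as if it had no AI, and hence that both halves of the ratio are wrong. No passage says so. The costed item is the immediate-read pathway, the design text defines routine care as including the qXR read, and some training may be a true increment: section 2 notes that giving results at once may call for communication training. Only an undefined term remains.

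**Conclusion.** The horizon point holds. A 60-day limit is too short for outcomes that run to diagnosis and the multidisciplinary decision, and the sole reason given does not justify it. Between 16% and 77% of the modelled mean difference is kept across the Table 7 scenarios; the 63 v 53 day case used in the sample-size text is the worst of them. The figures of about half undiagnosed and 438 of 900 belong to that case only.

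These sizes rest on exponential times, equal arms, a clock starting at the CXR, and equal eventual detection. The economic outcome ends at the multidisciplinary decision, so if that comes after the diagnosis date used for planning, the loss would be larger.

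The comparator point holds only as an ambiguity to be closed, with no size attached. The Part A clinical endpoints are not affected.

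**What to change.** 1. **Horizon.** Set the main horizon to capture nearly all diagnoses and multidisciplinary decisions, and keep 60 days as a sensitivity analysis. Under 63 v 53 days, 180 days reaches 86% v 91% and 12 months 98% v 99%. Neither needs discounting, which the Protocol applies only after the first year. State when the clock starts.
2. **Late-imaged patients.** The study ends 12 months after first deployment and sets no follow-up period. With even intake (an assumption), only (365 − 180)/365 = 51% of patients would have 180 days by then, and almost none 12 months. State whether routine records will be extracted later, or how these patients will be censored or modelled.
3. **Comparator.** Name it as routine reporting with the qXR read available at reporting, as in sections 4.2 and 5. Cost what both arms use in both arms, and cost as incremental only what the immediate pathway adds. Label any comparison of AI with no AI as modelled from outside evidence.

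**Cost.** Mostly wording and a longer model. Table 6 already lists the dates of diagnosis, decision to treat and treatment start, and stage. It has no separate entry for the multidisciplinary meeting, so the Protocol should say which date stands for that decision. The price is some extrapolation, or a later extraction, for patients imaged late.
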